#### 3.2.3.4 Rationale for study endpoints (efficacy)

The primary aim of this study is to determine the efficacy of MEDI4736 (10 mg/kg Q2W via iv infusion) compared with placebo in terms of OS and PFS. Progression free survival may serve as a surrogate endpoint for OS when differences between treatment groups are of sufficient magnitude and clinically important ([FDA Guidance 2011](#), [Pazdur 2008](#)). In certain settings, the utility of survival as an endpoint may potentially be confounded by subsequent therapies. Specifically, there are currently a number of molecules, targeting the PD-1/PD-L1 pathway, in late-stage development in second- and third-line squamous NSCLC. It is anticipated that these agents may be approved or become available for use through expanded-access mechanisms or additional clinical studies while this study is ongoing. This poses challenges in being able to fully characterize effects on OS if patients subsequently receive these immunotherapeutic agents. However, given that tumour response to immunotherapy may differ from typical responses, both PFS and OS are co-primary endpoints with the study powered for OS.

Antitumour activity will be assessed according to RECIST v1.1 guidelines, with the understanding that in the context of post-radiation changes tumour assessment may be difficult and may need to be repeated over time to reach a clear determination regarding responses and/progressive disease (see Section 6.3). The co-primary analysis of PFS will be based on programmatically derived PFS based upon BICR assessments. Sensitivity analyses will also be performed using data from site Investigators tumour data from all scans based

upon RECIST 1.1 and site Investigator tumour data from all scans based upon RECIST 1.1 modified for confirmation of progression. Exploratory analysis will also be performed for data obtained from the BICR on a subset of 250 evaluable patients scans using irRC.

This is because the response to immunotherapy may differ from typical responses observed with cytotoxic chemotherapy including the following (per [Wolchok et al 2009](#)):

1. Response to immunotherapy may be delayed
2. Response to immunotherapy may occur after PD by conventional criteria
3. SD while on immunotherapy may be durable and represent clinical benefit.

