1.3 Number of Subjects

The sample size for this study was selected to be consistent with the research hypothesis as described in Section 1.2 of the CSP.

The two co-primary endpoints of this study are OS and PFS. To control for type-I error, a significance level of 2.5% will be used for analysis of OS and a significance level of 2.5% will be used for analysis of PFS. The study will be considered positive (a success) if either the PFS analysis results and/or the OS analysis results are statistically significant.

Approximately 702 patients will be randomised 2:1 to obtain 491 death events in the ITT population (70% maturity). The primary PFS analysis DCO will occur when it is expected that 458 PFS events have occurred (65% maturity). If the true PFS HR is 0.67, the study will provide at least 95% power to demonstrate a statistically significant difference for PFS with a 2-sided significance level of 2.5% in the ITT population; this translates to a 5-month benefit in median PFS over 10 months on placebo if PFS is exponentially distributed. The smallest treatment difference that would be statistically significant is a HR of 0.8. A recruitment period of approximately 22 months and a follow-up period of 14 months are expected for the PFS endpoint. Therefore it is anticipated that this PFS analysis could be performed approximately 36 months after the first patient has been randomised.

The primary OS analysis DCO will occur when it is expected that 491 OS events have occurred (70% maturity). If the true OS HR is 0.73, this number of death events will provide at least 85% power to demonstrate a statistically significant difference for OS, assuming a 2.5% 2-sided significance level in the ITT population; this translates to an 8-month benefit in median OS over 22 months on placebo if OS is exponentially distributed (Butts et al 2014). The smallest treatment difference that would be statistically significant is a HR of 0.81. A recruitment period of approximately 22 months and a follow-up period of 40 months are expected for the OS endpoint. Therefore it is anticipated that this OS analysis could be performed at approximately 62 months after the first patient has been randomised.

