3.2.1.1 Overall survival (OS)

OS is defined as the time from the date of randomisation until death due to any cause (i.e., date of death or censoring – date of randomisation + 1). Any patient not known to have died at the time of analysis will be censored based on the last recorded date on which the patient was known to be alive (SUR_DAT, recorded within the SURVIVE module of the eCRF).

Note: Survival calls will be made in the week following the date of DCO for the analysis, and if patients are confirmed to be alive or if the death date is post the DCO date these patients will be censored at the date of DCO. The status of ongoing, withdrawn (from the study) and “lost to follow-up” patients at the time of the final OS analysis should be obtained by the site personnel by checking the patient’s notes, hospital records, contacting the patient’s general practitioner and checking publicly-available death registries. In the event that the patient has actively withdrawn consent to the processing of their personal data, the vital status of the patient can be obtained by site personnel from publicly-available resources where it is possible to do so under applicable local laws.

Note that for any OS analysis performed prior to the final OS analysis, in the absence of survival calls being made, it may be necessary to use all relevant CRF fields to determine the last recorded date on which the patient was known to be alive for those patients still on treatment (since the SURVIVE module is only completed for patients off treatment if a survival sweep is not performed). The last date for each individual subject is defined as the latest among the following dates recorded on the CRFs:

- AE start and stop dates
- Admission and discharge dates of hospitalization
- Study treatment date
- End of treatment date
- Laboratory test dates
- Date of vital signs
- Disease assessment dates on RECIST CRF
- Start and stop dates of alternative anticancer treatment
- Date last known alive on survival status CRF
- End of study date

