3.2.1.2 Progression free survival (PFS)

PFS (per RECIST 1.1 as assessed by BICR) will be defined as the time from the date of randomisation until the date of the first objective disease progression or death (by any cause in the absence of progression) regardless of whether the patient withdraws from randomised therapy or receives another anti-cancer therapy prior to progression (i.e., date of PFS event or censoring – date of randomisation + 1). Patients who have not progressed or died at the time of analysis will be censored at the time of the latest date of assessment from their last RECIST 1.1 assessment. However, if the patient progresses or dies after 2 or more missed visits, the patient will be censored at the time of the latest RECIST 1.1 assessment prior to the two missed visits.

Given the scheduled visit assessment scheme (ie eight-weekly for the first 48 weeks then twelve-weekly thereafter) the definition of 2 missed visits will change. If the previous RECIST assessment is less than study day 274 (ie week 39) then two missing visits will equate to 18 weeks since the previous RECIST assessment, allowing for early and late visits (ie, 2 x 8 weeks + 1 week for an early assessment + 1 week for a late assessment = 18 weeks). If the two missed visits occur over the period when the scheduled frequency of RECIST assessments changes from eight-weekly to twelve-weekly this will equate to 22 weeks (ie,

take the average of 8 and 12 weeks which gives 10 weeks and then apply same rationale hence 2×10 weeks + 1 week for an early assessment + 1 week for a late assessment = 22 weeks). The time period for the previous RECIST assessment will be from study days 274 to 344 (ie week 39 to week 49). From week 49 onwards (when the scheduling changes to twelve-weekly assessments), two missing visits will equate to 26 weeks (ie 2×12 weeks + 1 week for an early assessment + 1 week for a late assessment = 26 weeks). If the patient has no visits or does not have baseline data they will be censored at study day 1 unless they die within 2 visits of baseline (16 weeks plus 1 week allowing for a late assessment within the visit window).

The PFS time will always be derived based on scan/assessment dates not visit dates.

PFS will also be obtained using the algorithm described above for the RECIST site investigator tumour data.

RECIST 1.1 assessments/scans contributing towards a particular visit may be performed on different dates. The following rules will be applied:

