The result from the initial model and the model containing additional covariates will be presented.

Additional covariates for this model will be age at randomization, sex, smoking status, stage of disease at study entry, histology, best response to prior anticancer therapy, WHO performance status, region and race.

The model will include the effect regardless of whether the inclusion of effect significantly improves the fit of the model providing there is enough data to make them meaningful.

Consistency of treatment effect between subgroups

Interactions between treatment and stratification factors will also be tested to rule out any qualitative interaction using the approach of [Gail and Simon 1985](#).

Impact of switching (crossover outside of this study) to immunotherapies (or other potentially active investigational agents) on OS analyses

Exploratory analyses of OS adjusting for the impact of subsequent immunotherapy or other treatment may be performed, if a sufficient proportion of patients switch.

Methods such as Inverse Probability of Censoring Weighting ([Robins 1993](#)), Rank Preserving Structural Failure Time ([Robins and Tsiatis 1991](#)), and other methods in development will be explored as appropriate. The decision to adjust and the final choice of methods will be based on a blinded review of the data and the plausibility of the underlying assumptions. Additional supportive analysis by censoring the treatments switchers at the time of initiation of subsequent therapy will also be conducted. These analyses are intended to further support the OS benefit and reimbursement appraisals.

Baseline and time-dependent characteristics will be explored, and summaries of baseline characteristics will be provided by treatment arm, splitting between those that have and haven't switched at the time of the analyses.

Subsequent therapies received after discontinuation of treatment will be summarised and listed by treatment group. Patients who subsequently received an immunotherapy agent or entered an immunotherapy trial will be summarised and listed by treatment arm according to line of subsequent therapy, i.e. immediately after immunotherapy or as a later line.

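### The only firmly worded OS switching analysis censors switchers with no weights specified, so its hazard ratio carries a bias whose direction and size cannot be known in advance

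*SAP*

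**What the plan says.** The Protocol, section 3.2.3.4, anticipates that other PD-1/PD-L1 agents in late development for second- and third-line use may become available during the study, and comments: "This poses challenges in being able to fully characterize effects on OS if patients subsequently receive these immunotherapeutic agents". It names no arm and gives no rate. The Protocol's OS methods (12.2.2.1) include no switching analysis.

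SAP 4.2.1.1 adds one, in three steps of different firmness:

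- Adjustment in general is optional: "Exploratory analyses of OS adjusting for the impact of subsequent immunotherapy or other treatment may be performed, if a sufficient proportion of patients switch". No threshold for a sufficient proportion is given.
- IPCW and rank-preserving structural failure time (RPSFT) models are named, "and other methods in development will be explored as appropriate". The choice rests on a blinded data review and on how plausible the assumptions are.
- Then: "Additional supportive analysis by censoring the treatments switchers at the time of initiation of subsequent therapy will also be conducted". No weights, covariates or caveat accompany this sentence.

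The purpose follows: "These analyses are intended to further support the OS benefit and reimbursement appraisals".

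The primary endpoint does not censor at switch. SAP 3.2.1.1 says: "OS is defined as the time from the date of randomisation until death due to any cause".

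**The concern.** A log-rank or Cox analysis that censors at the start of subsequent therapy estimates the no-switching effect only if switchers and non-switchers still at risk have the same prospects. Later-line therapy usually starts after progression, when the risk of death is much higher. Without weights, the analysis compares the hazard of death among patients who have not yet switched, a group depleted of progressed patients to a different degree in each arm.

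The SAP recognises this kind of problem elsewhere: in 4.2.1.2 it warns of informative censoring in the central-review PFS analysis. It gives no such warning here, although the least defensible of the listed methods has the firmest wording and the result is meant to support the OS benefit and reimbursement. At stake is an HR that could understate or overstate the effect and sit awkwardly beside a valid primary result.

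**Working it through.** **1. The plan's own figure.** SAP 1.3: 702 patients, 2:1, 491 deaths, two-sided 2.5%. "If the true OS HR is 0.73, this number of death events will provide at least 85% power".

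- Information: √(491 × 2/9) = 10.446; critical z = 2.241.
- Power = Φ(|ln 0.73| × 10.446 − 2.241) = Φ(1.046) = 85.2%.
- Smallest significant HR = exp(−2.241/10.446) = 0.807.

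Both agree with the plan (at least 85%; 0.81). The documents give no figure for the switching analysis.

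**2. Inputs for the bias check.** From SAP 1.3: median PFS 10 and 15 months, placebo median OS 22 months, 22 months' accrual, cut-off at 62 months. Assumed, because the documents are silent: 10% of PFS events are deaths; switching occurs 1 month after progression; the switch probability depends only on arm; the post-progression hazard is the same in both arms.

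- Hazard of a PFS event on placebo: ln 2/10 = 0.0693 per month, of which death without progression is 0.1 × 0.0693 = 0.0069.
- Post-progression hazard that gives a 22-month placebo median OS: 0.0745 per month, about 11 times 0.0069.

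**3. Why the direction varies.** Let w be the share of living patients in an arm who have progressed, had nobody switched, and p the share of progressors who switch. Ignoring the short delay, the progressed share among those still at risk after censoring is w(1 − p)/(1 − wp), that is, w multiplied by (1 − p)/(1 − wp).

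- If p is larger on placebo, the placebo hazard is cut more and the HR moves up, towards the null or harm.
- If p is equal but PFS is better on MEDI4736, w is larger on placebo, the factor is closer to 1 there, and the HR moves down, towards MEDI4736.

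**4. Censored HR.** Large-sample Cox results (600,000 simulated patients); true no-switching HR 0.723:

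| Switching, placebo / MEDI4736 | Censored, unweighted | IPCW |
|---|---|---|
| 20% / 10% | 0.745 | 0.725 |
| 30% / 8% | 0.792 | 0.725 |
| 40% / 10% | 0.830 | 0.726 |
| 60% / 20% | 0.916 | 0.725 |
| 40% / 40% | 0.686 | 0.726 |

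Direct numerical integration of the same model gives 0.723 with no switching and 0.745, 0.791, 0.830, 0.918 and 0.685 for the five rows. The log-HR error is ln(0.830/0.723) = +0.138 for 40%/10% and ln(0.686/0.723) = −0.053 for 40%/40%. With a shared frailty of variance 0.5 (true HR 0.804), the censored HR ranges from 0.775 to 1.073 and IPCW from 0.802 to 0.804.

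**5. Against ITT.** The ITT error depends on the later therapy's effect on death; the censored HR does not. For 40%/10%, no frailty, true HR 0.723, censored HR 0.830:

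| HR of switch therapy on death | ITT | Further from truth |
|---|---|---|
| 0.7 | 0.778 | censored |
| 0.5 | 0.841 | ITT |
| 0.35 | 0.916 | ITT |

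Over 40 scenarios (five switching patterns, four switch HRs from 0.7 to 0.2, with and without frailty), censoring was further from the truth in 21 and ITT in 19.

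**The case against.** **The analysis is supportive, untested and perhaps conditional.** It lies outside the multiplicity procedure in SAP 4.1.2, and no significance level is attached to it. The sentence may inherit the condition that opens the paragraph, that enough patients switch. It is described as additional to IPCW and RPSFT, and the SAP also plans baseline summaries by switching status. All of this stands and limits the weight of the point. It does not make the unweighted estimate valid: even on the conditional reading, it would accompany any adjustment without a caveat.

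**Switching need not follow progression.** The SAP foresees earlier therapy, since PFS is counted "regardless of whether the patient withdraws from randomised therapy or receives another anti-cancer therapy prior to progression". That is fair. Post-progression use is nevertheless the case that Protocol 3.2.3.4 describes.

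**Stronger readings that a reader might infer.** One is that unweighted censoring is always worse than ITT. Step 5 shows otherwise, and the documents give neither a switching rate nor a switch effect. Another is that the analysis inflates type I error. With no effect on PFS or OS and 40%/10% switching, the censored HR is about 1.15 to 1.18, but that assumes far more placebo switching in a double-blind trial (Protocol 5.4.1) with identical outcomes in both arms. With equal switching and no PFS effect there is no inflation, and the error in the unequal case points to harm, not to false benefit.

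**The IPCW results flatter the fix.** They use the true switching probabilities. Estimated weights will do less well, and fail if an important driver of switching is unmeasured.

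**Conclusion.** The point holds in a limited form. Naive censoring is the only switching analysis that the SAP words as definite, and where switching follows progression its HR is biased. Under the assumptions above, the bias is towards the null or harm if placebo patients switch more (0.830 against 0.723 at 40%/10%) and modestly towards MEDI4736 if switching is equal and PFS improves (0.686 against 0.723 at 40%/40%). It may be closer to or further from the no-switching HR than ITT is. Switching rates, switch timing, the share of PFS events that are deaths, and frailty are assumptions, so these figures show direction and plausible size; they are not forecasts. The primary ITT analysis of OS, its power and its error control are untouched.

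**What to change.** In SAP 4.2.1.1, replace the sentence on censoring switchers with wording such as:

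> Whenever OS is analysed with switchers censored at the start of subsequent therapy, the analysis will use inverse-probability-of-censoring weights estimated by arm from baseline covariates, time-dependent progression status and time since progression, and WHO performance status where available. Any unweighted version will be shown only beside the ITT and IPCW results, labelled as subject to informative censoring, and will not be cited as support for the OS benefit.

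The cost is a short SAP edit. IPCW is already named in that paragraph, and progression dates and subsequent therapy are already collected. The downsides are wider intervals, dependence on the weight model, and reliance on no unmeasured confounding. WHO performance status after discontinuation is only partly available: the footnotes to Protocol Tables 2 and 3 ask for extra readings where staff or circumstances allow, and Protocol 5.8.1 offers telephone follow-up to patients who decline visits. It should therefore be a covariate where recorded, with a stated rule for missing values.

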4.2.1.2 Progression free survival

PFS based upon the programmatically derived RECIST outcome using the BICR data (including all scans regardless of whether they were scheduled or not) will be analysed by stratified log-rank tests, the same methodology as described for the OS analyses.

The primary analysis of the co-primary endpoint, PFS, will occur when it is expected that 458 PFS events have occurred (65% maturity). PFS based upon the BICR data will be analyzed using a stratified log-rank test adjusting for the same factors as for OS. The effect of treatment will be estimated by the HR together with its corresponding (1-alpha adjusted)% CI and p-value for the full ITT population. Kaplan-Meier plots of PFS will be presented by treatment arm. Summaries of the number and percentage of patients experiencing a PFS event, and the type of event (RECIST 1.1 or death) will be provided along with median PFS for each treatment.

The assumption of proportionality will be assessed in the same way as for OS. The analysis will be based on the programmatically derived PFS using BICR data.

Supportive summaries/graphs

The treatment status at progression of patients at the time of analysis will be summarised. This will include the number (%) of patients who were on treatment at the time of progression,

the number (%) of patients who discontinued study treatment prior to progression, the number (%) of patients who have not progressed and were on treatment or discontinued treatment. This will also provide distribution of number of days prior to progression for the patients who have discontinued treatment.

The number of patients prematurely censored will be summarised by treatment arm. A patient would be defined as prematurely censored if they had not progressed (or died in the absence of progression) and the latest scan prior to DCO was more than one scheduled tumour assessment interval plus 2 weeks (10 weeks if time period between randomisation and DCO for that patient is 48 weeks or less; 14 weeks otherwise) prior to the DCO date.

Additionally, summary statistics will be given for the number of days from censoring to DCO for all censored patients.

A summary of the duration of follow-up will be summarised using median time from randomisation to date of censoring (date last known to be non-progressor) in censored (not progressed) patients only, presented by treatment group.

Additionally, summary statistics for the number of weeks between the time of progression and the last RECIST assessment prior to progression will be presented for each treatment group.

Summaries of the number and percentage of patients who miss two or more consecutive RECIST assessments will be presented for each treatment group.

All of the collected RECIST 1.1 data will be listed for all randomised patients. In addition, a summary of new lesions (i.e., sites of new lesions) will be produced.

Sensitivity Analyses

The following sensitivity analyses will be performed:

- Evaluation-Time bias

Sensitivity analyses will be performed to assess possible evaluation-time bias that may be introduced if scans are not performed at the protocol-scheduled timepoints. The midpoint between the time of progression and the previous RECIST assessment will be analysed using a stratified log-rank test, as described for the co-primary analysis of PFS. For patients whose death was treated as PFS event, the date of death will be used to derive the PFS time used in the analysis. This approach has been shown to be robust to even highly asymmetric assessment schedules ([Sun and Chen 2010](#)). To support this analysis, the mean of subject-level average inter-assessment times will be tabulated for each treatment. This approach will use the BICR data.

- Attrition bias

Attrition bias will be assessed by repeating the co-primary PFS analysis except that the actual PFS event times, rather than the censored times, of patients who progressed or died in the absence of progression immediately following two, or more, tumour assessments will be included. In addition, patients who take subsequent therapy prior to their last evaluable RECIST assessment or progression or death will be censored at their last assessment prior to taking the subsequent therapy. This analysis will be supported by a Kaplan-Meier plot of the time to censoring where the censoring indicator of the PFS analysis is reversed. This approach will use the BICR data.

- Ascertainment bias

Ascertainment bias will be assessed by analysing the site investigator data. The stratified log-rank test will be repeated on PFS using the site investigator data based upon RECIST. If there is an important discrepancy between the primary analysis using the BICR assessments and this sensitivity analysis using investigator assessments, then the proportion of patients with site but no central confirmation of progression will be summarised; such patients have the potential to introduce bias in the central review due to informative censoring. An approach that imputes an event at the next visit in the central review analysis may help inform the most likely HR value (Fleischer et al 2011), but only if an important discrepancy exists.

Disagreements between investigator and central reviews of RECIST progression will be presented for each treatment group. The summary will include the early discrepancy rate which is the frequency of central review declared progressions before the investigator review as a proportion of all central review progressions and the late discrepancy rate which is the frequency of central review declared progressions after the investigator review as a proportion of all discrepancies.

- Confirmation bias

An additional sensitivity analysis using the BICR data will be performed to determine the effect of confirmation of progression. The stratified log-rank test will be repeated on PFS using BICR data based upon RECIST modified for confirmation of progression. The HR and CI will be presented.

Subgroup/Additional Analysis

An exploratory analysis of PFS using the irRECIST 1.1 data provided by the BICR will be performed on the BICR analysis set. The stratified log-rank test will be repeated on PFS using the BICR based upon the irRECIST 1.1 data. The HR and CI will be presented.

Subgroup analyses and a forest plot will be generated comparing PFS between treatments in the same way as previously specified for OS. Unless there is a marked difference between the results of the statistical analyses of the PFS from the BICR data and that of the site investigator, this will only be performed upon the PFS endpoint using the BICR data based upon RECIST. No adjustment to the significance level for testing will be made since all these

subgroup and sensitivity analyses will be considered supportive of the primary analysis of PFS.

A forest plot illustrating the hazard ratio and the corresponding 95% confidence interval will be provided to compare the primary and sensitivity analyses of progression free survival.

The effect of covariates upon the HR estimate and the consistency of treatment effect between subgroups will be analysed for PFS using the same methods as those described for OS.

A further analysis of PFS (using investigator assessed RECIST) may be performed at the time of the OS analyses, if requested by health authorities.

Time to first subsequent therapy or death (TFST)

For supportive purposes, the time to the start of subsequent therapy will be analysed using the same methodology and model as that used for the co-primary analysis of PFS. The HR for the treatment effect together with its 95% CI will be presented. In addition, a Kaplan-Meier plot of the time to the start of subsequent therapy will be presented by treatment arm and the time between progression and starting subsequent therapy will be assessed based upon the investigator data defined date of progression. This will be summarised per treatment arm but no formal comparisons will be made. No multiplicity adjustment will be applied as this is viewed as a supportive endpoint.

In patients who received a subsequent cancer therapy, a summary table of first subsequent cancer therapies by treatment arm will be provided.

